#### **7.1.5.6 Survival Follow-up**

Participants who experience confirmed disease progression or start a new anticancer therapy, will move into the Survival Follow-Up Phase and should be contacted by telephone if needed to assess for survival status until death, withdrawal of consent, or the end of the trial, whichever occurs first.

### **7.2 Assessing and Recording Adverse Events**

#### **7.2.1 Definition of an Overdose for This Protocol and Reporting of Overdose to Merck**

For purposes of this study, an overdose of pembrolizumab will be defined as any dose of 1,000 mg or greater ( $\geq 5$  times the indicated dose). No specific information is available on the treatment of overdose of pembrolizumab. In the event of overdose, the participant should be observed closely for signs of toxicity. Appropriate supportive treatment should be provided if clinically indicated.

If an adverse event(s) is associated with (“results from”) the overdose of a Merck product, the adverse event(s) is reported as a serious adverse event, even if no other seriousness criteria are met.

If a dose of Merck’s product meeting the protocol definition of overdose is taken without any associated clinical symptoms or abnormal laboratory results, the overdose is reported as a non-serious Event of Clinical Interest (ECI), using the terminology “accidental or intentional overdose without adverse effect.”

All reports of overdose with and without an adverse event must be reported within 2 working days hours to Merck Global Safety. (Attn: Worldwide Product Safety; [contact])

#### **7.2.2 Reporting of Pregnancy and Lactation to Merck**

Although pregnancy and infant exposure during breast feeding are not considered adverse events, it is the responsibility of investigators or their designees to report any pregnancy or lactation in a participant (spontaneously reported to them) that occurs during the study.

Pregnancies and infant exposures during breastfeeding that occur after study therapy starts but before treatment allocation/randomization must be reported by the Investigator if they cause

the participant to be excluded from the trial or are the result of a protocol-specified intervention, including but not limited to washout or discontinuation of usual therapy, diet, placebo treatment or a procedure.

Pregnancies and infant exposures during breastfeeding that occur from the time of treatment allocation through 7 months following cessation of the product, or 30 days following cessation of treatment if the participant initiates new anticancer therapy, whichever is earlier, must be reported by the investigator. All reported pregnancies must be followed to the completion/termination of the pregnancy. Pregnancy outcomes of spontaneous abortion, missed abortion, benign hydatidiform mole, blighted ovum, fetal death, intrauterine death, miscarriage and stillbirth must be reported as serious events (Important Medical Events). If the pregnancy continues to term, the outcome (health of infant) must also be reported.

Such events must be reported within 2 working days to Merck Global Safety. (Attn: Worldwide Product Safety; [contact])

### **7.2.3 Adverse Event**

According to ICH guidelines (Federal Register. 1997; 62(90):25691-25709) and 21 CFR 312.32, IND Safety Reports, and ICH E2A, Definitions and Standards for Expedited Reporting, an adverse event is defined as follows:

An adverse event is any untoward medical occurrence in a clinical investigation subject administered a medicinal product and which does not necessarily have a causal relationship with this treatment. An AE can therefore be any unfavorable and unintended sign (including an abnormal laboratory finding), symptom, or disease temporally associated with the use of a medicinal product, whether or not considered related to the medicinal product.

Abnormal laboratory values for laboratory parameters specified in the study should not be recorded as an adverse event unless an intervention is required (repeat testing to confirm the abnormality is not considered intervention), the laboratory abnormality results in a serious adverse event or the adverse event results in study termination or interruption/discontinuation of study treatment.

Medical conditions present at screening (i.e., before the study treatment is administered) are not adverse events and should not be recorded on adverse event pages of the CRFs. These medical conditions should be adequately documented on the subject chart. However, medical conditions present at baseline that worsen in intensity or frequency during the treatment or post-treatment periods should be reported and recorded as adverse events.

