### 4.2 Secondary Objective(s)

(1) **Objective:** To assess the frequency and severity of toxicity according to Common Terminology Criteria for Adverse Events version 5.0 (CTCAE v5.0) in patients treated with aMVAC and pembrolizumab

(2) **Objective:** To evaluate the feasibility of neoadjuvant aMVAC and pembrolizumab as measured by the rate of patients able to receive RC within 10 weeks from completion of study therapy.

(3) **Objective:** To assess the recurrence-free survival (RFS), defined as time from trial enrollment to recurrence or death at the two-year time point in patients treated with aMVAC and pembrolizumab

(4) **Objective:** To assess the absolute and percentage (%) change in CD8+ TIL density at RC compared to pre-treatment TURBT

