#### 5.3.3 Dose Modifications for aMVAC chemotherapy (recommendations only; actual decisions for chemotherapy will be based on the best clinical judgment and institutional guidelines, if applicable)

##### 5.3.3.1 Hematological Toxicity

Grade 1 and Grade 2 toxicities will be accepted without dose interruption or dose modification. However, for grade 2 neutropenia on day 1 of any chemotherapy cycle (absolute neutrophil count  $1-1.5 \times 10^9/L$ ), dose reduction to 75% dose of methotrexate, vinblastine and doxorubicin is recommended.

If a patient experiences Grade 3 hematological toxicity on day 1 of any chemotherapy cycle, study chemotherapy will be held until toxicity has resolved or  $\leq$  Grade 1. For grade 3 neutropenia on day 1 of any chemotherapy cycle (absolute neutrophil count

1-1.5x10^9/L) that resolves to  $\leq$  Grade 1 within 4 weeks, dose reduction to 66% dose of methotrexate, vinblastine and doxorubicin is recommended. If the Grade 3 toxicity does not resolve to  $\leq$  Grade 1 within 4 weeks, all study chemotherapy may be **permanently discontinued**. Pembrolizumab may continue in that case as per physician discretion based on attribution.

If the patient experiences Grade 4 treatment related hematologic toxicity, all study chemotherapy may be **permanently discontinued** regardless of the time to resolution  $\leq$  Grade 1. Pembrolizumab may continue in that case as per physician discretion based on attribution.

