## 8.0 STATISTICAL CONSIDERATIONS

The primary objective is to evaluate the pCR rate at RC with neoadjuvant aMVAC and pembrolizumab in non-UC predominant histologic variants. A pCR rate of 8% or less would be considered of insufficient activity based on historical data for TURBT alone. A design with 91% exact power to rule out an 8% pCR rate at the 1-sided 4% exact level, if the true pCR rate is 36% would require 17 patients. The observation of at least 4 patients with pCR (23.5% pCR rate) would be considered evidence to rule out a pCR rate of 8%. The calculations are based on the one-arm binomial calculator at [www.swogstat.org](http://www.swogstat.org).

The anticipated duration of accrual is 17-26 months (1 patient every 30-45 days) given low prevalence (10-25%) of non-UC predominant histologic variants. However, if after the study has been active for 18 months and 8 or fewer patients have been enrolled, the accrual goal may be modified to target a total of 14 patients. In this case, the design would have 96% exact power to rule out an 8% pCR rate at the 1-sided 10% exact level, if the true pCR rate is 40%. The observation of at least 3 patients with pCR (21.4% pCR rate) would be considered evidence to rule out a pCR rate of 8%.

Secondary objectives include an evaluation of the frequency and severity of toxicity of the regimen, evaluation of recurrence-free survival at 2 years and TIL density at RC. With 17 patients, binary proportions can be estimated to within 24% with 95% confidence. Any toxicity with true prevalence of 10% or greater is likely to be observed with an 83% chance. The feasibility of the regimen will be evaluated by the percentage of patients able to undergo RC within 10 weeks from end of study therapy. This proportion along with 95% confidence intervals will be evaluated. The relationship (or lack thereof) between any delay of RC beyond 10 weeks and study therapy will be described.

Distributions of time-to-event outcomes will be estimated using the method of Kaplan-Meier. The rates at specified time points will use these estimates and the associated 95% confidence intervals. Continuous outcomes, such as TIL density and PD-L1 expression levels will be summarized by means, medians, and quantiles. Changes in continuous outcomes (such as CD8, TILs) will be evaluated as both absolute and percentage change. Descriptive statistics will also be used when needed.

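### A toxicity table built from AE records would under-count laboratory toxicity, because Section 7.2.3 keeps no-action laboratory abnormalities off the AE record and Section 8.0 plans no table from the laboratory values

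*Combined protocol and SAP*

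**What the plan says.** Section 4.2, objective 1, reads: "To assess the frequency and severity of toxicity according to Common Terminology Criteria for Adverse Events version 5.0". It covers all grades and makes no exception for laboratory toxicity.

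Section 7.2.3 first defines an AE broadly, as "any unfavorable and unintended sign (including an abnormal laboratory finding), symptom, or disease temporally associated with the use of a medicinal product". It then narrows what goes on the record: "Abnormal laboratory values for laboratory parameters specified in the study should not be recorded as an adverse event unless an intervention is required". Repeat testing does not count as an intervention. A laboratory finding is also recorded if "the laboratory abnormality results in a serious adverse event or the adverse event results in study termination or interruption/discontinuation of study treatment".

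Section 5.3.3.1, on chemotherapy, says: "Grade 1 and Grade 2 toxicities will be accepted without dose interruption or dose modification". The one stated exception is Grade 2 neutropenia at the start of a cycle, for which a dose reduction is recommended.

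Section 8.0 says of toxicity: "Any toxicity with true prevalence of 10% or greater is likely to be observed with an 83% chance". It does not say that haematology or chemistry results will be graded by CTCAE or tabulated, although Section 6.1 schedules both tests at the treatment, pre-operative and post-operative visits.

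**The concern.** The objective asks how often toxicity of each grade occurs. The recording rule admits a protocol-specified laboratory abnormality only if something was done about it or something serious followed. A table built from those records shows laboratory toxicity that triggered action, which is a narrower quantity than CTCAE frequency.

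The regimen is four cytotoxic drugs plus pembrolizumab, and marrow, renal and hepatic changes seen on blood tests are an important part of its toxicity. If the table is read as CTCAE frequency, rates of laboratory toxicity will look too low, and grade distributions will be tilted towards events that prompted action. The committees that review adverse events under Section 9.2 would see the same filtered record, and that section states that there are no interim stopping rules.

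**Working it through.** **1. Which laboratory events reach the AE record**

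| Laboratory event | Governing text | Recorded as an AE? |
|---|---|---|
| Isolated Grade 1 change | Table 6 defines Grade 1 as needing no intervention | Generally no |
| Grade 1-2 anaemia or thrombocytopenia | Section 5.3.3.1: accepted without action | Generally no |
| Grade 2 neutropenia at the start of a cycle | Section 5.3.3.1: dose reduction recommended | Unclear: Section 7.2.3 names interruption and discontinuation, not reduction, and leaves open whether a reduction is an intervention |
| Grade 3 haematological toxicity at the start of a cycle | Section 5.3.3.1: chemotherapy held | Yes, by the interruption exception |
| Immune-related AST/ALT or bilirubin elevation, or nephritis, Grade 2 or higher | Table 3: pembrolizumab withheld or permanently discontinued | Yes |
| CrCl below 45 mL/min | Section 5.3.3.2: hold | Yes |
| CrCl 45-59 mL/min | Section 5.3.3.2: administration modified | Unclear, as for dose reduction |
| Higher-grade change at the week-3 visit, only observed | Week 3 is a pembrolizumab-only visit (Table 2), so the start-of-cycle chemotherapy rule does not apply | No, unless another exception applies |
| Higher-grade change at the pre-operative or post-operative visit, only observed | Last planned dose is at week 6, so after a completed course no study treatment is left to interrupt | No, unless it needs intervention or results in an SAE |

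The loss is therefore mainly at Grade 1-2, with some higher-grade events at visits where no treatment decision follows.

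**2. The plan's own figure**

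Inputs from Section 8.0: n = 17, true prevalence p = 0.10.

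P(at least one case) = 1 − (1 − p)^n = 1 − 0.9^17 = 0.833.

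This reproduces the stated 83%. The formula counts every occurrence as observed.

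**3. What incomplete recording would do**

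Let c be the share of patients with a given laboratory toxicity whose event meets an exception. The documents give no value for c, so the range below is an assumption. The expected recorded rate is c × p, and

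P(at least one recorded case) = 1 − (1 − 0.10c)^17.

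| c (assumed) | Expected recorded rate | P(at least one recorded), n = 17 |
|---|---|---|
| 1 | 10% | 83.3% |
| 0.75 | 7.5% | 73.4% |
| 0.5 | 5% | 58.2% |
| 0.25 | 2.5% | 35.0% |
| 0 | 0% | 0% |

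Put the other way, keeping an 83% chance would need a true prevalence of 0.10/c: 13.3% at c = 0.75, 20% at c = 0.5 and 40% at c = 0.25. The direction is certain for any toxicity with c below 1. The position on this scale is not known.

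The figure is also tied to 17 patients. Section 8.0 adds that "the accrual goal may be modified to target a total of 14 patients" if accrual is slow. With full recording the chance is then 1 − 0.9^14 = 77.1%.

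**4. The primary design**

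No laboratory record enters the pCR rule. At 17 patients with at least 4 pCRs, the exact one-sided level is 4.2% and power 91.1%. At 14 patients with at least 3, they are 9.6% and 96.0%. Both agree with Section 8.0.

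**The case against.** The strongest reply is that the recording rule catches much of what matters. Table 3 withholds pembrolizumab from Grade 2 for immune-related hepatic and renal events, Section 5.3.3.2 holds below a renal threshold, and Section 5.3.3.1 holds chemotherapy for Grade 3 haematological toxicity at the start of a cycle. On-treatment blood counts are scheduled only at treatment visits, so many of them fall where a hold would apply. This stands, and it rules out a blanket claim that higher-grade laboratory toxicity goes unrecorded. It has limits: Table 3 covers immune-related events only, Section 5.3.3 is headed as recommendations, and neither reaches an observed change at week 3 or after the last dose.

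A reader might infer that the 83% is wrong. It is not. It is a generic sample-size statement, it is computed correctly, and it holds for non-laboratory toxicity and for any laboratory toxicity whose recordable form has 10% prevalence. For laboratory toxicity recorded only in part, it is an upper bound.

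It can also be said that this is a descriptive secondary endpoint in a small pilot, and that Section 8.0 already allows descriptive statistics when needed. The first is true and limits the importance of the point. The second permits a laboratory table but commits to none, so the gap remains.

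**Conclusion.** The point holds in a limited form. Following Section 7.2.3 and tabulating AE records would under-count laboratory toxicity against objective 1, mainly at Grade 1-2 and for higher-grade changes that are only observed. This rests on two readings: that the toxicity table will come from the AE record, since no other source is planned, and that the Section 7.2.3 rule will be applied as written.

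The size cannot be derived. The 73.4%, 58.2% and 35.0% in the working illustrate assumed capture shares and should not be quoted as estimates for this trial. The documents also do not support inferring that Grade 2 or higher hepatic and renal toxicity is generally lost, or that the trial's decision rule is affected. The pCR design stands, and no statistical toxicity boundary exists for the under-count to bias.

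**What to change.** Keep the Section 7.2.3 rule for AE forms; it reasonably limits routine entries. Add to Section 8.0, for objective 1:

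- Scheduled haematology and chemistry results will be graded by CTCAE v5.0, whether or not they were recorded as AEs.
- Worst post-baseline grade and shift from baseline will be reported per patient, beside the recorded AEs.
- The 83% statement assumes that every occurrence is recorded.

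No new tests are needed. The cost is programming and possibly some laboratory data entry for 14-17 patients, because the protocol does not say that every laboratory value reaches the eCRF. Reported toxicity rates will look higher. Between-cycle nadirs would still be missed, since no scheduled blood count targets them, and the table should say so.

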### **7.2.4 Serious Adverse Events**

An adverse event should be classified as an SAE if it meets one of the following criteria

Fatal	Adverse event results in death.
Life threatening:	The adverse events placed the subject at immediate risk of death. This classification did not apply to an adverse event that hypothetically might cause death if it were more severe.
Hospitalization:	It required or prolonged inpatient hospitalization. Hospitalizations for elective medical or surgical procedures or treatments planned before enrollment in the treatment plan or routine check-ups are not SAEs by this criterion. Admission to a palliative unit or hospice care facility is not considered to be a hospitalization.
Disabling/incapacitating	Resulted in a substantial and permanent disruption of the subject's ability to carry out normal life functions.
Congenital anomaly or birth defect:	An adverse outcome in a child or fetus of a subject exposed to the molecule or treatment plan regimen before conception or during pregnancy.
Medically significant:	The adverse event did not meet any of the above criteria but could have jeopardized the subject and might have required medical or surgical intervention to prevent one of the outcomes listed above.

### 7.2.5 Unexpected Adverse Event

An unexpected adverse event is defined as an event that has a nature or severity, or frequency that is not consistent with the applicable Investigator Brochure, or the prior medical condition of the subject or other treatment given to the subject. “Unexpected,” as used in this definition, refers to an adverse drug experience that has not been previously observed and reported in preclinical or clinical studies rather than an experience that has not been anticipated based on the pharmacological properties of the study drug.

### 7.2.6 Monitoring and Recording Adverse Events

All AEs will be assessed by the Investigator or qualified designee and recorded in the CRFs. The Investigator should attempt to establish a diagnosis of the event on the basis of signs, symptoms and/or other clinical information. In such cases, the diagnosis should be documented as the adverse event and/or serious adverse event and not described as the individual signs or symptoms. The following information should be recorded:

- Description of the adverse event using concise medical terminology
- Description as to whether or not the adverse event is serious, noting all criteria that apply
- The start date (date of adverse event onset)
- The stop date (date of adverse event resolution)
- The severity (grade) of the adverse event
- A description of the potential relatedness of the adverse event to study drug, a study procedure, or other causality

- The action taken due to the adverse event
- The outcome of the adverse event

Subjects will be followed for safety per iRAE clinical guidelines and standard clinical procedure if they terminate early or experience a non-serious AE considered to be possibly or definitely related to study treatment.

### **7.2.7 Grading Adverse Event Severity**

All AEs will be graded in severity according to the NCI Common Terminology Criteria for Adverse Events (CTCAE) Version 5.0 (Table 6). If a CTCAE criterion does not exist, the Investigator should use the grade or adjectives: Grade 1 (mild), Grade 2 (moderate), Grade 3 (severe), Grade 4 (life-threatening), or Grade 5 (fatal) to describe the maximum intensity of the adverse event.

### **7.2.8 Attribution of an Adverse Event**

Association or relatedness to the study agent will be assessed by the Investigator as follows:

- Definite: The event follows a reasonable temporal sequence from exposure to the investigational agent, has been previously described in association with the investigational agent, and cannot reasonably be attributed to other factors such as the subject's clinical state, other therapeutic interventions or concomitant medications; AND the event disappears or improves with withdrawal of the investigational agent and/or re-appears on re-exposure (e.g., in the event of an infusion reaction).
- Probable: The event follows a reasonable temporal sequence from exposure to the investigational agent and has been previously described in association with the investigational agent OR cannot reasonably be attributed to other factors such as the subject's clinical state, other therapeutic interventions or concomitant medications.
- Possible: The event follows a reasonable temporal sequence from exposure to the investigational agent but could be attributable to other factors such as the subject's clinical state, other therapeutic interventions or concomitant medications.
- Unlikely: Toxicity is doubtfully related to the investigational agent(s). The event may be attributable to other factors such as the subject's clinical state, other therapeutic interventions or concomitant medications.

Unrelated: The event is clearly related to other factors such as the subject's clinical state, other therapeutic interventions or concomitant medications.

For general AE assessment, an AE is considered related if it is assessed as definitely, probably, or possibly related; unrelated if it is assessed as unlikely related or unrelated.

### **7.2.9 Adverse Event Recording Period**

AEs will be monitored and recorded in study-specific case report forms (CRFs) from the time of first exposure to an investigational product in this study (i.e., the start of the first \ infusion). AEs with an onset date prior to the first exposure to an investigational product will not be recorded.

## **7.2.10 Adverse Event Reporting Requirements**

### **7.2.10.1 Reporting to Merck**

The Sponsor-Investigator or designee must report events to Merck (the financial sponsor of the study) as outlined in the contract.

For the time period beginning at study therapy initiation through the safety follow up visit following cessation of treatment, or 30 days following cessation of treatment if the participant initiates new anticancer therapy, whichever is earlier, any serious adverse event, or follow up to a serious adverse event, including death due to any cause whether or not related to the Merck product, must be reported within 2 working days to Merck Global Safety.

Additionally, any serious adverse event, considered by an Investigator who is a qualified physician to be related to Merck product that is brought to the attention of the investigator at any time following consent through the end of the specified safety follow-up period specified in the paragraph above, or at any time outside of the time period specified in the previous paragraph also must be reported when feasible to Merck Global Safety.

All participants with serious adverse events must be followed up for outcome.

SAE reports and any other relevant safety information are to be forwarded to Merck Global Safety [contact].

A copy of all IND Safety Reports and Annual Progress Reports is submitted as required by FDA., The Sponsor-Investigator will submit a copy of these reports to Merck & Co., Inc. (Attn: Worldwide Product Safety; [contact]) at the time of submission to FDA.

